5.10. Maintenance of Randomization and Blinding

5.10.1. Maintenance of Randomization

Patient randomization codes will be maintained in a secure location at the service provider contracted to generate the codes. At the time of analysis (after the end of study), after receiving unblinding request from Teva statistician, the service provider will provide the unblinded IMP assignment according to the processes defined in the relevant Standard Operating Procedure (SOP).

5.10.2. Blinding and Unblinding

Double-Blind Treatment Phase

In case of a serious adverse event, pregnancy, or in cases when knowledge of the IMP assignment is needed to make treatment decisions, the investigator may unblind the patient's IMP assignment as deemed necessary, mainly in emergency situations, through specialized access in the IRT system. Breaking of the treatment code can always be performed by the investigator without prior approval by the sponsor; however, the sponsor should be notified that the code was broken, but the patient treatment assignment should not be revealed to the sponsor.

When a blind is broken, the patient will be withdrawn from the study, and the event will be recorded on the eCRF. The circumstances leading to the breaking of the code should be fully documented in the investigator's study files and in the patient's source documentation.

Assignment of IMP should not be recorded in any study documents or source document.

In blinded studies, for an adverse event defined as a suspected unexpected serious adverse reaction (SUSAR) (ie, reasonable possibility, see Section 7.1.4), Global Patient Safety and Pharmacovigilance (GPSP) may independently request that the blind code be broken (on a case-by-case basis) to comply with regulatory requirements. The report will be provided in an unblinded manner for regulatory submission. If this occurs, blinding will be maintained for the investigator and for other personnel involved in the conduct of the study and the analysis and reporting of the data.

Open-Label Extension Phase

The open-label extension phase has no blinding.

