Patient fulfills the following criteria for CM in prospectively collected baseline information during the 28-day baseline period:

- headache occurring on ≥ 15 days

- on ≥ 8 days, fulfilling any 1 of the following:
 - ICHD-3 diagnostic criteria C and D for 1.1 Migraine without aura ([Appendix I](#))
 - ICHD-3 criteria B and C for 1.2 Migraine with aura ([Appendix I](#))
 - probable migraine (a migraine subtype where only 1 migraine criterion is missing)
 - triptan or ergot derivative used to treat established headache.

EM is defined as:

The patient fulfills the following criteria for EM in prospectively collected baseline information during the 28-day baseline period:

- headache occurring ≥ 4 days but < 15
- on ≥ 4 days, fulfilling any 1 of the following:
 - ICHD-3 diagnostic criteria C and D for 1.1 Migraine without aura ([Appendix I](#))
 - ICHD-3 criteria B and C for 1.2 Migraine with aura ([Appendix I](#))
 - probable migraine (a migraine subtype where only 1 migraine criterion is missing)
 - triptan or ergot derivative used to treat an established headache

At the randomization visit (day 1), patients will be randomly assigned to 1 of 2 treatment groups of 225 mg sc fremanezumab or placebo in a 1:1 ratio. Patients will receive their assigned study treatment on visit 2 (day 1), visit 3 (day 29), and visit 4 (day 57) and then continue into the open-label extension phase in which all patients will receive a quarterly dose of 675 mg sc fremanezumab on visit 5 (day 85). Investigators can contact patients in between study visits per their clinical judgment.

[figure not shown]
Patients who complete all scheduled visits will have procedures and assessments performed at visit 6 (end of treatment). Patients who withdraw from the study before completing the 24-week treatment phase will have visit 6 (end of treatment) procedures and assessments performed at their final visit.

Study procedures and assessments with their time points are shown in [Table 4](#). The study schematic diagram is shown in [Figure 1](#).

The end of study is defined as the last visit (end-of-treatment/early withdrawal visit [visit 6]) of the last patient.

The study duration will be approximately 24 months, from approximately September 2019 (first patient screened) to approximately August 2021 (last visit of the last patient).

Figure 1: Overall Study Schematic Diagram

EOT = end of treatment; PBO = placebo; sc = subcutaneous; V = visit.

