4.3. Withdrawal Criteria and Procedures for the Patient

Each patient is free to withdraw from the study or discontinue from IMP at any time, without prejudice to their continued care. Patients must be withdrawn from the IMP if any of the following events occur:

1. Patient withdraws consent or requests discontinuation from the IMP or withdrawal from the study for any reason.
2. Patient develops an illness that would interfere with his/her continued participation.
3. Patient is noncompliant with the study procedures and assessments or administration of IMPs in the opinion of the investigator.
4. Patient takes prohibited concomitant medications or receives prohibited therapies as defined in this protocol.
5. A female patient has a confirmation of pregnancy during the study from a positive urine pregnancy test.
6. The sponsor requests withdrawal of the patient.
7. Patient experiences an adverse event or other medical condition that indicates to the investigator that continued participation is not in the best interest of the patient.

Patients should be treated with standard of care after withdrawal from or termination of the study as appropriate.

Investigators should attempt to obtain information on patients in the case of withdrawal from the study or discontinuation from IMP. Results of any evaluations and observations, together with a narrative describing the reason(s) for withdrawal from the study or discontinuation from IMP, must be recorded in the source documents. The electronic case report form (eCRF) must document the primary reason for withdrawal from the study or discontinuation from IMP.

See [Appendix F](#) for information regarding how the study will define and address lost to follow-up patients to help limit the amount and impact of missing data.

If the reason for withdrawal from the study or discontinuation from IMP is an adverse event and/or clinically significant abnormal laboratory test result, monitoring will be continued as applicable (eg, until the event has resolved or stabilized, until the patient is referred to the care of a health care professional, or until a determination of a cause unrelated to the IMP or study procedure is made). The specific event or test result (including repeated test results, as applicable) must be recorded on both the source documentation and the eCRF; both the adverse events page and the relevant page of the eCRF will be completed at that time.

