7.1.2. Recording and Reporting of Adverse Events

For recording of adverse event, the study period is defined for each patient as the time period from signature of the ICF to the end of the follow-up period. The follow-up period of recording of adverse events is defined as 12 weeks after the last dose of IMP. The period for reporting treatment-emergent adverse events is defined as the period after the first dose of IMP is administered and until end of follow-up period on day 169 (± 3 days).

All adverse events that occur during the defined study period must be recorded on both the source documentation and the eCRF, regardless of the severity of the event or judged relationship to the IMP. For serious adverse events, the serious adverse event form must be completed and the serious adverse event must be reported immediately (Section 7.1.5.3.1). The investigator does not need to actively monitor patients for adverse events after the defined period. Serious adverse events and adverse events of special interest occurring in a patient after the defined study period should be reported to the sponsor if the investigator becomes aware of them, following the procedures described in Section 7.1.5.3.1.

At each contact with the patient, the investigator or designee must question the patient about adverse events by asking an open-ended question such as "Have you had any unusual symptoms or medical problems since the last visit? If yes, please describe." All reported or observed signs and symptoms will be recorded individually, except when considered manifestations of a medical condition or disease state. A precise diagnosis will be recorded whenever possible. When such a diagnosis is made, all related signs, symptoms, and any test findings will be recorded collectively as a single diagnosis on the eCRF and, if it is a serious adverse event, on the serious adverse event form.

The clinical course of each adverse event will be monitored at suitable intervals until resolved, stabilized, or returned to baseline; or until the patient is referred for continued care to a health care professional; or until a determination of a cause unrelated to the IMP or study procedure is made.

The onset and end dates, duration (in case of adverse event duration of less than 24 hours), action taken regarding IMP, treatment administered, and outcome for each adverse event must be recorded on both the source documentation and the eCRF.

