7.2. Pregnancy

Any female patient becoming pregnant during the study will discontinue IMP. All pregnancies of women participating in the study and female partners of men participating in the study that occur during the study or within at least 6 months after the last dose of IMP are to be reported immediately to the individual identified in the Clinical Study Personnel Contact Information section of this protocol, and the investigator must provide the sponsor (LSO/CRO) with the completed pregnancy form. The process for reporting a pregnancy is the same as that for reporting a serious adverse event but using the pregnancy form (Section 7.1.5.3). The investigator is not required to report patients who are found to be pregnant between the screening visit (V1) and randomization visit (V2 on day 1), provided no protocol-related procedures were applied.

All female patients (or female partners of men participating in the study) who become pregnant will be monitored for the outcome of the pregnancy (including spontaneous or elective abortion). Female partners of men participating in the study who become pregnant will be asked to sign an ICF. If the pregnancy continues to term, the outcome (health of the infant up to 8 weeks of age), including details of birth and presence or absence of any birth defect, congenital abnormalities, or maternal and newborn complications, will be reported to the sponsor. Any complication of pregnancy during the study and any complication of pregnancy that the investigator becomes aware of after withdrawal from the study will be reported as an adverse event or serious adverse event, as appropriate.

If the pregnancy in the woman participating in the study and/or the female partners of men participating in the study does not continue to term, one of the following actions will be taken:

- For a spontaneous abortion, report as a serious adverse event.
- For an elective abortion due to developmental anomalies, report as a serious adverse event.
- For an elective abortion **not** due to developmental anomalies, report on the pregnancy form; do not report as an adverse event.

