9.2. Analysis Sets

9.2.1. Intent-to-Treat Analysis Set

The intent-to-treat (ITT) analysis set will include all randomized patients.

In the ITT analysis set, treatment will be assigned based on the treatment to which patients were randomized, regardless of which treatment they actually received.

Data collected from patients after treatment discontinuation will be included in the ITT analysis set.

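### An investigator code-break in the double-blind phase withdraws the patient from the study, so scheduled safety assessment ends before the protocol's own 12-week adverse event window closes

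*Protocol*

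**What the plan says.** Protocol Section 5.10.2, under its double-blind heading, gives the investigator the option of unblinding a patient. The occasions are introduced with "In case of a serious adverse event, pregnancy, or in cases when knowledge of the IMP assignment is needed to make treatment decisions". The same sentence leaves the need to the investigator's judgment and says that emergencies are the main use. The next paragraph carries no exception: "When a blind is broken, the patient will be withdrawn from the study, and the event will be recorded on the eCRF".

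Three other sections bear on the same patients:

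- **Section 4.3** treats leaving the study and stopping drug as separate steps: "Each patient is free to withdraw from the study or discontinue from IMP at any time". Its mandatory list opens with "Patients must be withdrawn from the IMP if any of the following events occur". The list includes a confirmed pregnancy and an adverse event that makes continuing contrary to the patient's interest. A code-break is not on it.
- **Section 7.2**: "Any female patient becoming pregnant during the study will discontinue IMP". It does not mention leaving the study.
- **Section 7.1.2**: "The follow-up period of recording of adverse events is defined as 12 weeks after the last dose of IMP".

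Section 3.1 gives the practical effect of withdrawal. Patients who leave before the 24 weeks are complete "will have visit 6 (end of treatment) procedures and assessments performed at their final visit". Table 4 (footnote a) and Appendix B add one suicidality phone call a week for two weeks. Nothing is scheduled after that.

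**The concern.** For a pregnancy or a serious adverse event, Sections 4.3 and 7.2 stop at study drug. If the investigator also breaks the code, Section 5.10.2 takes the patient out of the study as well. The reason for stopping drug may be identical in two patients, yet only the unblinded one must lose the remaining visits.

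The loss is tied to outcome. Patients reach this rule because something has already gone wrong, so any shortfall in detecting new or delayed events is concentrated in them. Safety tables built from scheduled assessments are then incomplete in an informative way, even if the numbers are small. The trial has no data monitoring board (Section 5.10.3), enrolls patients with active depressive symptoms, and has suicidal ideation and behavior on the eC-SSRS as a safety endpoint (Section 2.1). SAP Section 4.4 also drops early-termination data from the by-visit summaries, keeping them only in the last-assessment summaries.

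**Working it through.** The plan states no figure for this point. The check sets the visit schedule against the adverse event window.

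**Inputs.** Double-blind doses on days 1, 29 and 57; open-label dose on day 85; visits on days 29, 57, 85 and 169 (Protocol Table 4). Adverse event window: 12 weeks = 84 days after the last dose (Section 7.1.2).

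**The plan's own end date first.** For a completer, the last dose on day 85 plus 84 days gives day 169, which is visit 6. A completer therefore has a full assessment on the day the window closes.

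**A patient withdrawn after a code-break.** Window end = last dose day + 84. If the final visit falls between that dose and the next planned one, 28 days later, the days of window left afterwards run from 84 − 28 = 56 up to 84.

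| Last dose | Window closes | Days left after final visit | Scheduled visits lost inside the window |
|---|---|---|---|
| Day 1 | 1 + 84 = day 85 | 56 to 84 | Days 29, 57, 85 |
| Day 29 | 29 + 84 = day 113 | 56 to 84 | Days 57, 85 |
| Day 57 | 57 + 84 = day 141 | 56 to 84 | Day 85 |

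In the first row, day 85 is the closing day itself, so the ±3-day visit allowance can put that visit on either side. Day 169 lies outside the window in every row.

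**Worked example.** Last dose on day 29; code-break and early-termination visit both on day 30 (assumed). Days of window left: 113 − 30 = 83. The two weekly calls reach about day 30 + 14 = 44. Visits lost inside the window: days 57 and 85. Section 1.2.2.1 puts the median time to peak concentration at 5 to 7 days after a subcutaneous dose, that is days 34 to 36. In this example the last laboratory, ECG and vital sign assessments come before the peak.

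**What continues after withdrawal.** Adverse events that led to withdrawal are monitored until resolved, stabilized, referred or judged unrelated (4.3, 7.1.2). Pregnancies are followed to outcome (7.2). Serious events learned of later are to be reported (7.1.2, 7.1.5). Section 7.1.2 also requires an adverse event question at every contact, which arguably extends to the two suicidality calls.

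**What stops after those calls.** Laboratory tests, ECG, vital signs, eC-SSRS and any scheduled occasion to ask about new events.

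**The case against.** The strongest reply is that the sections do not strictly conflict. Sections 4.3 and 7.2 set a minimum, stopping drug, and Section 5.10.2 adds a further step for unblinded patients; a site can comply with both. Section 3.4 already allows the investigator or sponsor to withdraw anyone from the study. That is correct as far as it goes. It does not explain why unblinding should end safety data collection, nor how recording to 12 weeks is to be achieved once there are no visits.

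Several stronger readings are tempting and should be resisted:

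- *Every serious adverse event or pregnancy ends participation.* Unblinding is optional and mainly for emergencies, and the rule covers only the double-blind phase.
- *All safety follow-up stops, or only the triggering event is followed.* The early-termination visit is a full assessment, and the duties listed in the working remain. Section 7.1.2 defines the recording period for each patient without making it conditional on staying in the study.
- *The days without a visit measure the harm.* Every completer also goes 84 days without a scheduled visit, from day 85 to day 169. The difference is the closing visit, plus the one to three visits in the table.
- *The analysis plan depends on these data.* Protocol Section 9.2.1 says "Data collected from patients after treatment discontinuation will be included in the ITT analysis set", but that concerns data already collected and schedules nothing. SAP Section 3.1.1 omits it, the SAP prevails where the two differ, and safety uses the safety sets. Section 7.1.7, on deviations because of an adverse event, does not mention unblinding. Neither section adds much.

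One objection stands and shapes the fix. The protocol has no explicit schedule for a patient who is off drug but still in the study, and it uses the terms loosely: starting a prohibited therapy means withdrawal from study drug in Section 4.3 but from the study in Section 9.7. Editing 5.10.2 alone may not secure follow-up.

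**Conclusion.** The point holds in a limited form. Section 5.10.2 attaches study withdrawal to a code-break, while Sections 4.3 and 7.2 require only stopping drug for pregnancy or adverse events. Systematic detection of new events then ends with 56 to 84 days of the 84-day window remaining and one to three scheduled visits inside it lost. This assumes that the final visit takes place between the last double-blind dose and the next planned one.

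The documents give no code-break rate, so any patient count, or any effect on power or bias, would be a guess. The number is probably small. The case for acting is that the loss is selected by harm and cheap to avoid, not that it threatens the trial's conclusions.

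Whether an unblinded patient should stop study drug is a clinical matter on which this point takes no position. A reader might also infer that sponsor safety unblinding for a SUSAR triggers withdrawal. The withdrawal sentence follows the investigator's code-break paragraph, and the separate SUSAR paragraph keeps the investigator blinded, so the text does not establish that. It does not exclude it either.

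**What to change.** Reconcile Protocol Section 5.10.2 with Sections 4.3, 7.1.2 and 7.2:

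1. State the consequence of a code-break for study drug, which is the sponsor's clinical decision, separately from its consequence for data collection.
2. Provide that, unless consent is withdrawn, the safety assessments already scheduled and adverse event recording continue through the existing 12-week window.
3. Flag efficacy ratings made after the code-break as unblinded.
4. State whether the withdrawal sentence is meant to cover a SUSAR unblinding by the sponsor's safety department in which the investigator stays blinded.
5. Put matching wording in Table 4 and Appendix B, so that a patient off drug but in the study has a defined schedule.

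The cost is a short protocol amendment with the usual ethics and authority approvals, across about 13 countries and 65 centers, so it is best combined with another amendment. The assessments are ones already planned, and the analysis has to carry a few unblinded later ratings.

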5.10.3. Data Monitoring Committee

There will be no Data and Safety Monitoring Board in this study.

5.11. Total Blood Volume

The total blood volume to be collected for each patient in this study is approximately 64.2 mL for scheduled tests. Details on total blood volume are provided in [Appendix J](#).

6. ASSESSMENT OF EFFICACY

Data from any efficacy assessments performed after the specified time will not be collected on the eCRF; in the event, however, that such data are collected, these data will not be analyzed.

6.1. Assessments of Efficacy

See [Appendix B](#) for a detailed description of assessments and procedures. Questionnaires and the headache diary will be collected with an electronic handheld device.

6.1.1. Electronic Headache Diary

Patients will keep a daily headache diary to record the number of migraine days and headaches days they experience. These diary entries will be reviewed at clinic visits on visit 2 (randomization), visit 3 (day 29), visit 4 (day 57), visit 5 (day 85), and visit 6 (day 169) (see [Table 4](#)).

The primary efficacy endpoint (and secondary and exploratory efficacy endpoints as well) will be derived from headache variables collected daily using an electronic headache diary device. Eligible patients will receive comprehensive training from site personnel on the use of the electronic headache diary device. Site personnel will also instruct patients on the requirement for timely and daily completion of the electronic diary. Approximately 75% compliance is needed after the randomization period. Site personnel will monitor patient's compliance that approximately 75% diary entry is met during the double-blind treatment phase and open-label extension phase.

On each day, the patient will be asked to record diary data for the previous 24-hour period. Patients may be asked about their performance at work, at school, and when doing household chores (ie, functional assessments). Patients who report headache on the previous day will answer questions about the headache (ie, the number of hours with headache, presence of associated symptoms, and use of acute migraine medications). Additional details regarding the questions that the patients will answer can be found in the electronic headache diary training manual.

If a patient fails to complete the diary for the preceding day, the patient will be prompted to enter the missed day's information the next time he/she accesses the electronic diary provided no more than 48 hours have elapsed since completion of that day. If more than 48 hours have elapsed since completion of a diary day, the patient will not be allowed to enter diary information for that day, and it will be considered a missed day.

Rating of headache severity and duration of headache for each day will be completed in the electronic diary. Overall headache duration will be recorded numerically (in hours) as well as number of hours with headache of at least moderate severity.

If headache is reported, then headache severity will be subjectively rated by the patient as follows:

- mild headache

- moderate headache
- severe headache

Patients will also record whether photophobia, phonophobia, nausea, and/or vomiting are present, and they will record any migraine medications (name of drug, number of tablets/capsules, and the dose in milligrams per tablet/capsule) taken on each day.

